To achieve the project aims, a prospective, longitudinal, in-depth design was employed across all three sub-studies. Twenty-four women with a history of severe EDs were interviewed twice: the first interview occurred during pregnancy (between weeks 9 and 40), and the second approximately four to six months postpartum. Semi-structured interviews explored the participants' perspectives, perceptions, and meanings attributed to their experiences related to food and body image. Supplementary data, including standardised diagnostic interviews (e.g. the EDE and EDE-Q), were gathered at both time points to establish diagnostic accuracy using DSM-5 criteria.

A semi-structured, participant-centred 'experience interview' was employed to gather data for all three sub-studies. A total of 24 women were interviewed at two time points, resulting in 48 interviews. Each participant engaged in two meetings, during which they received introductory information, participated in a semi-structured interview, and completed the EDE-Q (Fairburn & Beglin, 2008) and the EDE interview (Fairburn et al., 2008). The total duration for these sessions ranged from four to five hours, culminating in 206 hours of recorded material across all interviews.

Given the distinct nature of the questions posed in the three sub-studies, three different data analysis methods were employed (Masoodi, 2017). These methods facilitate the identification of patterns within and across participants' experiences and perspectives to address the research project's aims. Significant differences exist between Ideal Type (IT) analysis, Interpretative Phenomenological Analysis (IPA), and Grounded Theory (GT) in terms of selection, analysis, and reporting methods (e.g. constructed ITs and trajectories versus actual

experiences). These differences proved beneficial given the varied research focus of the studies.

Study 1: Bodies out of control: Relapse and worsening of eating disorders in pregnancy. Methods: Semi-structured interview/standardised interviews for diagnostic evaluation for DSM-5 diagnosis. Participant selection: 23 of 24 pregnant women with a history of Eds. 23. Interviews. Analysis: Ideal type (IT) analysis.

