Study 2: IVF-induced pregnancy and early motherhood among women with a history of severe eating disorders. Methods: Semi-structured interview/standardised interviews for diagnostic evaluation for DSM-5 diagnosis. Participant selection: Seven of the 24 women with a history of Eds and IVF backgrounds interviews from pregnancy to postpartum. 14 interviews.

Study 3: Trajectories of severe eating disorders through pregnancy and early motherhood. Methods: Semi-structured interview/standardised interviews for diagnostic evaluation for DSM-5 diagnosis. Participant selection: All 24 women with a history of Eds. Interviews from pregnancy to postpartum. 48 interviews. Analysis: Elements of Strauss' grounded theory (GT) analysis.

Study I: Ideal type analysis

IT analysis provides a structured approach for examining and comparing various aspects of experiences by simplifying them into distinct categories and concepts (Stapley et al., 2021). For this analysis, data from all participants at time point 1 (pregnancy) were utilised. Of the 24 participants, 23 reported either a worsening of or a relapse in EDs during pregnancy. Consequently, the experiences related to this worsening and/or relapse were further explored among these 23 participants.

The research questions for Study I ([name] et al., 2022) were: 1. How do women with a history of EDs experience pregnancy? 2. How do they understand and describe the worsening, relapse, and perceived triggers of these changes?

IT analysis (Weber, 1978) was selected to address these questions, as it allows for the identification of patterns among a group of women exhibiting considerable variation. This choice was informed by the limited empirical knowledge concerning how women with a history of EDs experience pregnancy and ED pathology. A heterogeneous sample was employed, not solely based on diagnoses but also considering background factors such as length of illness, whether participants were first-time mothers or had previous pregnancies, and experiences related to abortion, IVF, and trauma. IT analysis was thus used to encapsulate the most relevant experiences through ITs.

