Study I sought to uncover similarities and differences within and across the dataset regarding the participants' views and experiences (Ayres et al., 2003). Through IT analysis, the women's accounts were described within their contexts, while also highlighting the variations and patterns that may exist across their experiences (Ayres et al., 2003). Thus, IT analysis was employed to compare each participant's experiences of worsening or relapse, serving as a tool for interpretation and understanding of these occurrences, and for generating new insights regarding pregnancy in the context of EDs.

Key features of IT analysis include in-depth descriptions of participant groups, comparisons among groups and individuals through material deconstruction, hypothesis formation regarding thoughts and behaviours, and subsequent reconstruction of the material into qualitative cluster analyses.

Steps of the analysis in study 1

Five steps were inspired by IT analysis (Stapley et al., 2021):

1. Following the bottom-up principle (Richard, 2015; Seidel & Kelle, 1995), all text from time point one was transcribed and re-read. This process involved examining each line of the transcripts to capture meaning, compare data for similarities and differences, and list elements pertinent to the research questions. Active coding facilitated engagement with the data, encouraging questions, interpretations, and comparisons of experiences. Detailed notes from the interview experiences, including reflections on the significance of participants' accounts, were summarised. Of the 24 participants, 23 identified bodily changes as a challenge, noting significant deterioration or the re-emergence of EDs. Consequently, further analysis focused solely on experiences and perspectives related to the worsening or relapse of eating pathology.

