6. Four phenomena were identified: '*anxiousness and fear*', '*shame and guilt*', '*sexual maladjustment*', and '*non-disclosure of eating problems*' (see Section 5.3). These phenomena were named based on the content of the participants' experiences. The emerging themes were organised according to three phases: 'IVF', 'Pregnancy', and 'Motherhood'.

Study III: Grounded theory

GT emphasises the development of theory through systematic analysis of qualitative data (Charmaz, 2014; Corbin & Strauss, 2008; Glaser & Strauss, 1967). It identifies common themes regarding change across individuals and captures how participants' experiences evolve over time. A key feature of GT is its interpretative and systematic approach to data analysis (McCann & Polacsek, 2018; Strauss & Corbin, 1998). All 24 participants from both time points were included in this analysis.

The research questions for Study III ([name] et al., 2024) were: 1. How do women with a history of severe EDs experience their eating pathology during the process from pregnancy to postpartum? 2. Is it possible to identify different trajectories through pregnancy and early motherhood based on these experiences?

To address these questions, elements of GT, as inspired by Strauss (Corbin & Strauss, 2008), were employed to construct a model depicting the trajectories of ED pathology among all participants from pregnancy to postpartum. The aim was to uncover processes and structures related to experiences of ED pathology during these periods. Coherence and internal consistency patterns were sought, alongside consideration of differences in experiences across multiple cases. GT is an inductive methodology that seeks to bridge the gap between research and theory (Glaser & Strauss, 1967). Selected elements of GT provide a

theoretical framework for understanding a complex phenomenon, with emphasis placed on individual perspectives that yield valuable data for developing a theoretical sample (Strauss & Corbin, 1998).

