4. Constant comparison through the collection, transcription, analysis, and comparison of summaries facilitated the identification of patterns, themes, and categories (Charmaz, 2014; Corbin & Strauss, 2008). The examination of how women experienced ED pathology during pregnancy and postpartum, along with the interrelation of different themes, was addressed. The constant comparative method, initially proposed by Glaser and Strauss (1967) and later refined by Strauss (Corbin & Strauss, 2008), emphasises that the researcher should oscillate between the open coding (steps 1 and 2) and axial coding (step 3) processes multiple times before progressing to selective coding (steps 4 and 6) (Strauss & Corbin, 1998). This active coding process engaged the data, prompting questions, interpretations, and comparisons of experiences. The interplay between these steps facilitated the emergence of robust statements or concepts and verified the significance of a potentially crucial core trajectory (Corbin & Strauss, 2008). New data were continuously compared with previously collected information, including transcriptions and notes, to refine and adjust the emerging trajectories (Glaser & Strauss, 1967). This comparison process ensured that the modelled trajectories were grounded in the data and accurately represented the participants' experiences (Glaser & Strauss, 1967). Different categories emerged based on factors such as diagnosis, whether the mothers were undergoing IVF and distinctions between first-time and subsequent mothers.
5. The experiences related to different trajectories were validated against the original texts through confirmatory and selective coding (Corbin & Strauss, 2008). Three structural components were identified: precursors, triggers, and protective factors. Refer to Table 5 for details on these components and related quotations. Precursors were factors present before the women became pregnant, which they deemed salient in navigating pregnancy and early motherhood. Participants described various precursors (e.g. *personality characteristics, body-related precursors, precursors related to role-model affinities, familial transmission, attitudes towards pregnancy, the number of births, and earlier history of EDs*).

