Triggers were specific events associated with participants' experiences of relapse or exacerbation of EDs. For instance, a participant stated, '*Issues about weight had not been bothering me for the last few years* (precursor), *but when I got pregnant so quickly, I lost control*' (trigger), '*I want to be the perfect mother*' (precursor), and '*When I got pregnant, nothing went as I planned it*' (trigger). External triggers were identified (e.g. *negative comments on body or weight and lack of support*). Others were events that originated from within the participants (e.g. *changes in appearance, the body being an alien, feelings of lack of success, intensified exercising*).

Protective factors encompassed experiences and events that women associated with positive coping strategies during pregnancy and early motherhood, as well as improvements in their eating pathology over time.

6. The interrelations between the higher-order constructs (*precursors, triggers, and protective factors*) were examined to capture the complexity of participants' narratives. Experiences were described longitudinally, spanning from before pregnancy through pregnancy, childbirth, and the postpartum period. These experiences were organised into five trajectory constructs, representing the minimum necessary constructs to describe women's perceptions of their ED trajectories into motherhood.
7. Constructs closely reflecting participants' descriptions of their experiences were developed within an atheoretical framework, utilising elements from GT. The trajectory constructs were labelled based on their content, leading to the identification of short descriptions: *the mastering mother*, in which an ED pathology seems to be absent through pregnancy and early motherhood; *the succeeding mother*, in which an ED worsens during pregnancy, but reduces during early motherhood; *the inadequate mother*, in which ED

pathology worsens before pregnancy, through pregnancy, and during early motherhood; *the depressed mother*, in which the ED subsides during pregnancy, but worsens during early motherhood; and *the overwhelmed mother*, in which the ED worsens during pregnancy and early motherhood. Based on variations within these constructs, three overarching constructs representing five types of trajectories were extracted, with participants potentially belonging to one or two different trajectories.

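### Does the count of 23 of 24 women worsening or relapsing in pregnancy (Study I) contradict the *mastering* trajectory in Study III?

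*Combined protocol and SAP*

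**What the plan says.** Study I works from the first interview: "For this analysis, data from all participants at time point 1 (pregnancy) were utilised". Under Data analysis, that interview falls between weeks 9 and 40 of pregnancy. The result is given twice. Study I: Ideal type analysis says "Of the 24 participants, 23 reported either a worsening of or a relapse in EDs during pregnancy", and step 1 of Steps of the analysis in study 1 says "Of the 24 participants, 23 identified bodily changes as a challenge, noting significant deterioration or the re-emergence of EDs". Study I then continues with those 23 women.

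Study III: Grounded theory takes the whole sample: "All 24 participants from both time points were included in this analysis". Step 4 of its analysis says that constant comparison ensured that "the modelled trajectories were grounded in the data and accurately represented" what the women had experienced. Step 7 gives short descriptions of five trajectories. Two matter most here: *mastering*, "in which an ED pathology seems to be absent through pregnancy and early motherhood", and *depressed*, "in which the ED subsides during pregnancy, but worsens during early motherhood". The other three (*succeeding*, *inadequate*, *overwhelmed*) all have the eating disorder worsening in pregnancy. Step 7 also allows a woman to belong to one trajectory or to two.

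The visible text gives no number of women per trajectory and does not say where the 24th woman was placed.

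**The concern.** The two statements concern the same women and the same pregnancies. If all but one reported that the disorder worsened or returned while pregnant, a trajectory defined by its apparent absence throughout has almost nobody left to describe. *Depressed* raises a similar question, since it has the disorder easing in pregnancy.

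This could matter to a user of the results. Step 6 presents the five trajectories as the smallest set that describes the women's courses. The Study III text expects the framework to inform tailored support and later quantitative work. *Mastering* is the only trajectory without eating disorder pathology at any stage. A reader would want to know whether it rests on one woman, on none, or on several placed more loosely than the wording suggests.

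**Working it through.** **Inputs.** 24 women, two interviews each (Data analysis); 23 with worsening or relapse in pregnancy (Study I: Ideal type analysis, and step 1 of the study 1 analysis); all 24 in Study III (Study III: Grounded theory); trajectory descriptions (step 7 of the study III analysis).

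**The plan's own counts.** 24 × 2 = 48 interviews and, for the seven IVF women, 7 × 2 = 14. Both agree with the text. The 23 is an observed count and cannot be derived from anything else, but it is stated consistently.

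**Cap on *mastering*, reading its description as a strict rule.**
- Women without reported worsening or relapse: 24 − 23 = 1.
- Largest possible share in *mastering*: 1/24 = 4.2%. Share excluded: 23/24 = 95.8%.
- *Mastering* therefore holds 0 or 1 woman.

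**Can anything in the text raise the cap?**
- *Interview timing.* No. Worsening already reported at the first interview rules out absence through pregnancy. Later worsening in the 24th woman would lower the cap to 0.
- *Membership of two trajectories.* No, on the strict reading. Each of the other four includes worsening in pregnancy or early motherhood, so none can be combined with *mastering*.

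**Which trajectories are open to the 23?**

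| Trajectory | Course in pregnancy | Open to the 23? |
|---|---|---|
| Succeeding | worsens | yes |
| Inadequate | worsens | yes |
| Overwhelmed | worsens | yes |
| Depressed | subsides | yes, if it worsened and then eased in the same pregnancy |
| Mastering | seems absent | no |

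For *depressed*, the easing may come before or after the first interview. Study I counts what was reported about the pregnancy, not status on the interview day. A woman seen late, up to week 40, could report early worsening that had already eased. The number in *depressed* cannot be bounded from the text.

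**Are the statements compatible?** Place the 24th woman in *mastering* and spread the 23 over the other four, with those in *depressed* having worsened and then eased. Every statement is then true as written. There is no contradiction, even on the strictest reading.

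**The case for a change.** The strongest case for a change is that the tension is real and that the text which might ease it does not do so directly. Data analysis contrasts constructed types and trajectories with actual experiences, but only in general terms. The Design section declares a realist rather than a constructivist stance, and step 4 claims accurate representation, so two statements about the same pregnancies should agree visibly.

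Study III also hints at looser use of the labels. Step 1 lists codes for improvement and for putting the disorder on pause, and the pause quotation was plainly spoken before birth. The closing step says that triggers were addressed across all trajectories, although triggers are tied to relapse or exacerbation, which fits poorly with absence. A table of Study I status against trajectory, or a number per trajectory, would settle the matter cheaply if the data are still held.

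What stands is that, on a strict reading, the cap of one woman is correct and the visible text does not explain it. The rest does not lead to a change:

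- The hints of looser use count against reading step 7 as membership rules. The descriptions are short, *mastering* is worded with *seems*, the closing step calls the trajectories subjective, and two memberships are allowed. Strict placement is the reader's assumption.
- A construct supported by one woman is acceptable here. Informants says the aim is to identify different experiences, and sees a limitation where few women describe an experience and the descriptions are also thin. Research questions calls the deliverable on processes a hypothetical model.
- Counting cases per qualitative construct is debatable. A table isolating the one woman without worsening would sit uneasily with the Ethics assurance that published quotations cannot be linked to a person.
- Under Procedure, all data are deleted at completion. Rewording grounded constructs without the data would weaken their grounding.

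**Conclusion.** No change to the plan. The 23 of 24 and the *mastering* description can both be right. Read strictly, they imply that at most one woman (4.2%) is in *mastering*, which this design permits. Read as the hedged, overlapping descriptions that they appear to be, they imply no firm cap.

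The gap is one of reporting: how many women support each trajectory, and where the 24th belongs. The tables to which the text refers and the sub-study reports that it cites are not available here. The Study III report is the natural place for that detail, so its absence from this document does not show that it is missing. No coding step, sample or analysis rule would differ if it were written in.

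The cap of one assumes that women are placed by the step 7 wording for the index pregnancy, and that absence through pregnancy excludes anyone who reported worsening or relapse in it. The conclusion that no change is needed does not depend on those assumptions, because the statements are compatible even when both hold.

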2. Data were systematically and iteratively analysed using axial coding to identify key themes and concepts (Sbaraini et al., 2011). The complexity of each case was deliberated upon before achieving consensus on central themes and categories that encapsulated the participants' narratives rather than isolated factors (Corbin & Strauss, 2008). Corresponding to the main research questions in this study, all text excerpts addressing experiences and challenges related to ED pathology from pregnancy to postpartum were coded, based on contextual analysis rather than solely on participants' words. Themes and categories of trajectories emerged by defining meanings and making analytic interpretations of specific statements. For example, the statements '*I am disgusting*', '*I am fat*', and '*I feel like an alien*' were interpreted as differing aspects of the trajectory labelled '*overwhelmed mother*'.
3. Summaries for each participant were created to integrate data from various sources across two time points. These summaries captured the progression from pregnancy to postpartum, detailing participants' experiences regarding their journeys in and out of ED pathology. They facilitated the development of nuanced descriptions within and across cases, offering in-depth insights into how participants' thoughts, feelings, and behaviours related to body image, weight, and food evolved. Through the selective coding process, trajectories detailing movements in and out of ED pathology emerged.

4. Constant comparison through the collection, transcription, analysis, and comparison of summaries facilitated the identification of patterns, themes, and categories (Charmaz, 2014; Corbin & Strauss, 2008). The examination of how women experienced ED pathology during pregnancy and postpartum, along with the interrelation of different themes, was addressed. The constant comparative method, initially proposed by Glaser and Strauss (1967) and later refined by Strauss (Corbin & Strauss, 2008), emphasises that the researcher should oscillate between the open coding (steps 1 and 2) and axial coding (step 3) processes multiple times before progressing to selective coding (steps 4 and 6) (Strauss & Corbin, 1998). This active coding process engaged the data, prompting questions, interpretations, and comparisons of experiences. The interplay between these steps facilitated the emergence of robust statements or concepts and verified the significance of a potentially crucial core trajectory (Corbin & Strauss, 2008). New data were continuously compared with previously collected information, including transcriptions and notes, to refine and adjust the emerging trajectories (Glaser & Strauss, 1967). This comparison process ensured that the modelled trajectories were grounded in the data and accurately represented the participants' experiences (Glaser & Strauss, 1967). Different categories emerged based on factors such as diagnosis, whether the mothers were undergoing IVF and distinctions between first-time and subsequent mothers.
5. The experiences related to different trajectories were validated against the original texts through confirmatory and selective coding (Corbin & Strauss, 2008). Three structural components were identified: precursors, triggers, and protective factors. Refer to Table 5 for details on these components and related quotations. Precursors were factors present before the women became pregnant, which they deemed salient in navigating pregnancy and early motherhood. Participants described various precursors (e.g. *personality characteristics, body-related precursors, precursors related to role-model affinities, familial transmission, attitudes towards pregnancy, the number of births, and earlier history of EDs*).

Triggers were specific events associated with participants' experiences of relapse or exacerbation of EDs. For instance, a participant stated, '*Issues about weight had not been bothering me for the last few years* (precursor), *but when I got pregnant so quickly, I lost control*' (trigger), '*I want to be the perfect mother*' (precursor), and '*When I got pregnant, nothing went as I planned it*' (trigger). External triggers were identified (e.g. *negative comments on body or weight and lack of support*). Others were events that originated from within the participants (e.g. *changes in appearance, the body being an alien, feelings of lack of success, intensified exercising*).

Protective factors encompassed experiences and events that women associated with positive coping strategies during pregnancy and early motherhood, as well as improvements in their eating pathology over time.

6. The interrelations between the higher-order constructs (*precursors, triggers, and protective factors*) were examined to capture the complexity of participants' narratives. Experiences were described longitudinally, spanning from before pregnancy through pregnancy, childbirth, and the postpartum period. These experiences were organised into five trajectory constructs, representing the minimum necessary constructs to describe women's perceptions of their ED trajectories into motherhood.
7. Constructs closely reflecting participants' descriptions of their experiences were developed within an atheoretical framework, utilising elements from GT. The trajectory constructs were labelled based on their content, leading to the identification of short descriptions: *the mastering mother*, in which an ED pathology seems to be absent through pregnancy and early motherhood; *the succeeding mother*, in which an ED worsens during pregnancy, but reduces during early motherhood; *the inadequate mother*, in which ED

pathology worsens before pregnancy, through pregnancy, and during early motherhood; *the depressed mother*, in which the ED subsides during pregnancy, but worsens during early motherhood; and *the overwhelmed mother*, in which the ED worsens during pregnancy and early motherhood. Based on variations within these constructs, three overarching constructs representing five types of trajectories were extracted, with participants potentially belonging to one or two different trajectories.

- Condensed quotations from all interviews were utilised to illustrate the complexity of participants' experiences as grouped into a subjective trajectory. The three components (*precursors*, *triggers*, and *protective factors*) were addressed across all trajectories but exhibited significant variation among participants. These concepts were grounded in the data pertaining to the labels assigned to their experiences (e.g. *mastering*, *succeeding*, *inadequacy*, *depressed*, and *overwhelmed*). Through this process, the trajectories were tested and refined via further data collection and analysis (Glaser, 1978; Strauss & Corbin, 1998). Subsequently, these concepts were integrated into an empirical model elucidating the individual variation of ED pathology trajectories from pregnancy to postpartum concerning precursors, triggers, and protective factors.

Reference group: User representatives as co-researchers

In the pre-project phase, we will establish a reference group with relevant personal experience. In collaboration with the user organizations Counseling on Eating Disorders and the Eating Disorders Association, we have recruited a group of mothers who have had or have an eating disorder. The focus will be on experiences they themselves have had during and after pregnancy. The purpose is to get input to the interview guide and help to later validate the results. Research questions, analyzes and results will be discussed with the group during and finally during the project period.

Informants

We will use a heterogeneous sample. This has several causes. We currently know too little scientific to identify one scientifically and clinically interesting homogeneous group. Our clinical experience indicates that there can be great variation between different women in this life situation. In this round, we seek to identify different experiences one may have. Varied diagnoses have been chosen because we want to describe different courses, because these diagnoses are often unstable, and because we want to identify possible measures with different experiences and courses. Such diversity has great clinical relevance and has not been previously described scientifically. In practice, it facilitates the recruitment of informants. A disadvantage of using a heterogeneous sample is that each individual informant becomes relatively important. This is a small problem as long as the purpose is to identify different experiences. The limitation lies in the cases where a supposedly important experience is described in only one or very few informants and at the same time there is basically little depth and nuance in the descriptions. This is compensated to some extent by very high demands on the quality of the way we interview the informants. We know that some of those who have an eating disorder during childbirth may not have shown a symptomatic level during pregnancy. There can be many, and maybe even mean a different problem. Therefore, we have defined two groups of informants. We define one group of informants in pregnancy and follow longitudinally with two measurement times: in pregnancy and after birth. Another group of informants is defined after birth and interviewed about current and past experiences.

The number of informants for problem 1 will be determined on the basis of a saturation criterion where we include informants until after at least ten interviews, three subsequent interviews follow which do not add anything significantly new to the answer to the problems (30). Based on previous experience with similar surveys, the number of informants for each

issue is expected to be somewhere around 20 informants, ie about 40 informants. From these, a strategic choice will be made on issues 2 and 3. Strategic choice can mean looking for differences in order to obtain different prototype experiences. Recruitment of informants will take place continuously from the start of the project via a network. The project period has been extended to four years to get a sufficient number of informants.

Before further inclusion in the study, eating disorders are mapped with a revised version of the Eating Disorders Examination Questionnaire, EDE-Q adapted to pregnant women and women immediately after birth (16). The form is scored by the research fellow before further inclusion. EDE-Q is a self-completion form based on the "Eating Disorder Examination" (EDE) interview. EDE-Q measures the core symptoms of eating disorders. EDE-Q adapted to pregnant women and women immediately after birth is based on factor analysis. If the informant satisfies diagnostic criteria for a cut-off equivalent to ≥ 2.8 for an eating disorder, we will conduct a researcher-based interview, Eating Disorder Examination (EDE), for diagnosing the informant, and obtain standard background information. EDE is designed to assess the current condition, as well as to generate an operationalized defined eating disorder diagnosis. The interview is conducted after the experience interview.

The informants' background will be thoroughly documented. Background information will include data on age, gender, diagnosis, type of eating disorder, weight before, during and after pregnancy, onset of illness, first contact with the support system, relationships, first-time or multiple births. Background information is filled in by interviews after the experience interview.

Inclusion criteria will be that the woman is aged 20-40 and satisfies diagnostic criteria for anorexia nervosa, bulimia nervosa, overeating disorder or unspecified eating disorder (DSM-5). Exclusion Criteria will be people with additional problems related to ongoing psychosis, drug addiction or organic brain damage / disease because this will make it difficult to answer the research questions in this study.

Data collections

Information about the project will be disseminated, both orally and in writing via the network (see below). Before further inclusion in the study, eating disorders are mapped with a revised version of the Eating Disorders Examination Questionnaire, EDE-Q (28, 29) adapted to pregnant women and women immediately after birth (16). The questionnaire is completed by the informant with a representative from the network. The form is scored by the research fellow before further inclusion. EDE-Q is a self-completion form based on the interview "Eating Disorder Examination" (EDE). EDE-Q measures the core symptoms of eating disorders. EDE-Q adapted to pregnant women and women immediately after birth is based on factor analysis (15). If the informant satisfies diagnostic criteria for a cut-off equivalent to ≥ 2.8 for an eating disorder, we will conduct a researcher-based interview, Eating Disorder Examination (EDE), for diagnosing the informant, and obtain standard background information. EDE is designed to assess the current condition, as well as to generate an operationalized defined eating disorder diagnosis. The interview is conducted after the experience interview.

The informants' background will be thoroughly documented. Background information will include data on age, gender, diagnosis, type of eating disorder, weight before, during and after pregnancy, onset of illness, first contact with the support system, relationships, first-time or

multiple births. Background information is filled in by interviews after the experience interview.

Information about the issues is collected through a semi-structured, interactive face-to-face interview. The aim of the interviews is to get descriptions as precise and close to the participants' own experiences as possible. A semi-structured interview guide is designed in advance. The Interview Guide is developed in close collaboration with user representatives in the reference group and ensures that relevant input from the reference group is covered in the interview. The interview guide contains all the topics we want the interview to cover in advance. The interview guide is primarily a thematic guide and aims to prepare interviews as an instrument. It is also used as a summary and checklist for interviews at the end of the interview to ensure that all relevant topics are touched upon. The informants are thoroughly informed in advance about what the interview will be about and why, and how it will proceed. The better informed the informant is in advance, the better founded the voluntary participation. The actual interview takes the form of improvisation on the topics as it is natural from the dynamics that develop in the conversation. The informant can introduce their own relevant topics independently of the interview guide. The supervisors have published a double-digit number of scientific articles and trained thousands of clinicians and researchers with this method, which is informally called the "Experience Interview" developed by [name] (19, 21-23). The interviews are quality assured by a professional who is not directly involved, continuously listening through randomly selected sections of randomly selected interviews and providing guiding comments. The purpose of this is to ensure that consistency and validity in the interview format is maintained.

Data-analyze

All interviews are transcribed verbatim, stored, organized, coded and analyzed in the electronic software NVivo version 11. Data for problem 1 will be analyzed according to the Grounded Theory method (25, 26). The analysis involves eight phases such as categories, theoretical sampling, identification of similarities and differences between categories, open coding, focused coding, negative case analysis, theoretical sensitivity, theoretical sampling, theoretical saturation, memo writing. The analysis will be regularly discussed in the research group and continuously monitored by the main supervisor to ensure reliability and credibility. Data for issues 2 and 3 will be analyzed according to the IPA method (27). Repeated listening and reading of each interview is carried out to get an overview and context. Each text is then explored using open thematic coding according to the "bottom-up principle". Each interview is divided into text excerpts that are given a definition based on the content of meaning and distributed in a tree structure. The definitions of potential constructions are finally tested against the text by confirmation and selective coding according to the "top-down principle".

Validation of the results will take place through focus group interviews with informants from the survey with varying stories. The number and selection of focus group participants depends on the results. The participants will be briefly presented in advance with the most important results in writing. The results will then be presented orally to the group. The group will be asked to comment on the presentations. The purpose is to investigate whether the informants recognize their experiences as they have been analyzed, presented and illustrated, and possibly adjust and correct this. We make audio recordings of the focus group interview so that a person who is not directly involved in the project will listen through and check the conclusions the research fellow makes from the focus group interview.

Procedure

